2. PROTOCOL SYNOPSIS

This is a 50 patient, Phase 1/2a multi-center pilot study to test the safety and to describe the preliminary efficacy of intravenous administration of allogenic human cord tissue mesenchymal stromal cells (hCT- MSC) as an investigational agent, under U.S. INDs 19968 (Duke) and 19937 (U Miami) to patients with acute respiratory distress syndrome (ARDS) due to COVID-19 infection (COVID-ARDS). Patients will be eligible for treatment with 3 daily consecutive doses of hCT-MSC at 1 million cells/kg (max dose 100 million cells) in the phase 1 portion of the study or a fixed dose of 100 million cells daily x 3 days, 12-36 hours apart in the phase 2 portion of the study, if they have a

Confidential Page 8 of 32

confirmed diagnosis of COVID-19 and meet clinical and radiographic criteria for ARDS. The primary endpoint is short-term safety of hCT-MSC infusions given on this schedule. The key secondary endpoints are 28 day survival, an increase in PaO2/FiO2 ratio by 50% at 96 hours, days to hospital discharge to home or rehab, and number of days requiring mechanical or non-invasive ventilation or high flow nasal cannula.

The study will be executed in two phases. The first 10 consecutive patients will all receive investigational product. The second part of the study is a randomized, controlled trial in 40 additional patients. The overall aim of the study is to establish safety and to gain critical information as to whether patients with COVID-ARDS will benefit from MSC infusions. Results from the first 10 patients will be compared with concurrent outcomes utilizing standard of care treatments in participating hospitals and in published reports in the medical literature. Results from the additional 40 patients will be analyzed as a randomized placebo control trial. The trial is relying on focused eligibility of the participants (patients with ARDS), single cohort with short trial time (4 weeks), and simple assessment of clinical outcome (survival, improvement of ARDS). This is a sequential design in the sense that after the first 10 patients are evaluated a decision will be made by the PIs and the Data Safety Monitoring Board whether to proceed with the exploratory randomized portion of the study.

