The MSCs are manufactured from allogeneic cord tissue donated to the Carolinas Cord Blood Bank (CCBB) at Duke University. The CCBB is an FDA licensed public cord blood bank (licensed name DUCORD). Cord tissue is donated by mothers delivering healthy term male babies by Cesarean section, after written informed consent from the newborn infant's mother. Full donor screening and testing is performed in accordance with regulatory requirements (21CFR 1271). The hCT-MSCs will be manufactured in the Marcus Center for Cellular Cures in the Robertson GMP Cell Manufacturing Laboratory and the Clinical Research Cell Manufacturing Program (CRCMP) laboratory, Interdisciplinary Stem Cell Institute (ISCI), Miller School of Medicine, University of Miami. These hCT-MSCs are already being utilized in clinical trials to treat pediatric patients with autism spectrum disorder (IND 17313), cerebral palsy (IND 17921), hypoxic ischemic encephalopathy (IND 17313) and adults with osteoarthritis of the knee (IND18414). To date, over 210 doses of cells have been delivered to patients on these clinical trials with an excellent safety profile. At University of Miami, hCT-MSCs are used in the clinical trial to evaluate cytokine suppression in patients with chronic inflammation due to metabolic syndrome (IND 17324), 12 subjects in the pilot phase of the study had completed the dose without any treatment emergence SAE.

The rationale for using this approach for patients infected with COVID-19 is that ARDS, the rate-limiting complication impacting survival, is caused, at least in part, by a cytokine release syndrome (CRS) which results is severe immune dysregulation. Involved cytokines include IL-6, IL-8, IL-10, THP-1M, TNF-alpha, and others. MSCs have strong anti-inflammatory and immune-modulatory activities without apparent toxicity or further immunosuppression. Approximately 3-5 % of patients with COVID-19 develop ARDS which carries a very high mortality rate (30-60%) due to multi-system organ failure. Effective treatment of ARDS, the most feared complication of COVID-19, may convert the COVID-19 pandemic into a more manageable "flu-like" illness that every American is expected to experience, and most will survive, on an annual basis.

Confidential Page **9** of **32**

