3.6. CLINICAL EXPERIENCE WITH HCT-MSC

The current hCT-MSC product manufactured at Duke has been used in >90 children given >160 doses of 12-6 million hCT-MSC/kg intravenously, in approximately 54 adults with OA of the knee at 10-20M cells/dose given directly into the knee joint, and in 1 adult with bronchiectasis under an IND at a dose of 100 million total cells. In the proposed Phase 1 pilot portion of this study, we capped the dose per infusion at 100 million cells (total absolute dose) to follow conventions in an ongoing trial where absolute doses of 200 million cells appeared less effective than 100 million cells.

Confidential Page 13 of 32

The first 10 patients enrolled in this study were enrolled on the Phase 1, open label portion of this study. That cohort was fully enrolled with 8 patients treated at DUMC and 2 patients treated at the Boca Raton Regional Hospital. The median age of the patients was 61.5 years (29-79 years), 70% were female, 60% were Caucasian, and 30% were Hispanic. There were 4 SAEs reported in the trial, all resulting in death occurring on days 7, 27, 39, and 344 on study. None were deemed related to the MSC product. The MSC product infusions were well tolerated. There were no infusion related AEs or SAEs.

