6.1.1. LABORATORY AND CLINICAL EVALUATIONS

- Baseline is at enrollment (within 3 days- excluding COVID-19 PCR test which can obtained within 90 days to avoid repeat testing). Days post infusion are calculated from the first infusion. The "*" signifies that the test results from standard of care testing will be used however, they do not need to be obtained specifically for the study
- Height and weight with baseline physical examination
- Hematology: hemoglobin, hematocrit, platelet count, white blood cell (WBC) count, and WBC differential at baseline, day of infusion, Day 4, Day 7*, and Day 28*
- Coagulation: prothrombin time (PT)/aPTT/INR, D-dimer at baseline, Day 4*, and Day 28*
- Serum chemistry: CRP, ESR, AST, ALT, LDH, total bilirubin, alkaline phosphatase, total protein, albumin, sodium, potassium, chloride, carbon dioxide, calcium, blood urea nitrogen (BUN), creatinine, creatinine clearance and glucose at baseline, day of infusion*, Day 4*, Day 7*, and Day 28*
- Urinalysis*: pH, specific gravity, protein, glucose, ketones, blood, leukocyte esterase, and nitrite at baseline. Microscopy required only to follow-up clinically significant abnormal findings
- Chest x-ray* at baseline, Day 4*, Day 7*, and Day 28*
- ABGs prior, 1-4 hours after, Day 4*, Day 7*, and Day 28*
- COVID-19 PCR at baseline (do not repeat testing if obtained within 90 days of enrollment), day
 4*, 7*, and 28* post treatment
- Donor referral panel at baseline
- HLA typing (high resolution class I and class II) at baseline
- PRA (Anti-HLA antibodies) at baseline and day 28
- PaO2/FiO2 and oxygenation index endpoints (based on invasive or non-invasive mechanical ventilation or high flow nasal cannula use). To be done at Baseline, Day 1, Day 2, Day 4, and if on continued ventilation Day 7, and Day 14. PaO2/FiO2 may be calculated from an arterial blood gas or imputed from the SpO2/FiO2 table (Brown, et al. Chest 2016)
- Day 28 mortality
- Hospital discharge
- Invasive or non-invasive mechanical ventilation-free days and oxygen-free days
- Lung injury severity score (Murray) at Baseline, Day 1, Day 2, Day 4, Day 7, and Day 14. The
 most recent chest x-ray will be used to calculate the Murray score. For patients on pressure
 support mode ventilation, the peak pressure will be used in place of the plateau pressure to
 calculate compliance
- Any laboratory or imaging can be repeated outside the protocol requirements at the discretion of the treating physicians

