9.1.2 PHASE II

The second phase of the study will randomize 20 patients to placebo and 20 to hCT-MSC. The primary utility of the randomized phase of the trial is to evaluate the feasibility of conducting a larger, randomized trial comparing hCT-MSC to placebo, and to conduct descriptive analyses of efficacy outcomes. To enroll and randomize 90% of the eligible patients screened is a positive indicator of feasibility. The primary efficacy outcome of interest is time to recovery, defined as discharge from the hospital (alive) or remaining in the hospital without the need for supplemental oxygen or other COVID-related medical care. We expect based on previous research that 30% of patients in the placebo arm will recover at Day 28. This study is not powered to detect differences between arms except when those differences are large. Therefore, the approach to analysis will be descriptive. For example, with 20 patients per arm and no losses to follow-up, a 365-day accrual period and 28 days of follow-up per patient, the study would have 54% power to detect a doubling in the hazard of recovery with treatment (hazard ratio = 2.0) and 76% power to detect a hazard ratio of 2.5 using a log-rank test with 2-sided Type I error of 5%.

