9.4 ANALYSIS PLAN

Baseline characteristics of the participants will be summarized by study phase. The proportion of patients with infusion-related reactions and other unexpected product- related adverse reactions will be tabulated descriptively using CTCAE terminology. For Phase II, the time to recovery will be described using Kaplan-Meier plots comparing cumulative incidence in participants randomized to hCT-MSC with placebo. Results will be analyzed two ways: combining the two hCT-MSC arms vs. placebo, and each hCT-MSC arm separately vs. placebo. Other continuous, ordinal and binary outcomes will be analyzed in a similar fashion using appropriate descriptive statistics.

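### Section 9.4 gives no rule for deaths in the Kaplan-Meier curve of recovery; if deaths are censored, the curve overstates recovery by Day 28 and can hide a loss of recoveries

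*Combined protocol and SAP*

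**What the plan says.** Section 9.1.2 names the primary efficacy outcome of Phase II as "time to recovery, defined as discharge from the hospital (alive) or remaining in the hospital without the need for supplemental oxygen" or other COVID-related care. It expects that "30% of patients in the placebo arm will recover at Day 28" and says that "the approach to analysis will be descriptive".

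Section 9.4 gives the method: "the time to recovery will be described using Kaplan-Meier plots comparing cumulative incidence in participants randomized to hCT-MSC with placebo". The comparison is made twice: the two cell-product arms pooled against placebo (20 versus 20), and each product arm of 10 separately against placebo.

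Neither section states what happens in the curve to a patient who dies before recovering. Section 9.3 covers only analysis by assigned arm.

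The documents do expect deaths. The synopsis describes "ARDS which carries a very high mortality rate (30-60%) due to multi-system organ failure", and Section 3.6 reports four Phase I deaths among 10 patients, "all resulting in death occurring on days 7, 27, 39, and 344 on study". Survival is handled apart from recovery. The synopsis says "The key secondary endpoints are 28 day survival" and Section 6.1.1 lists "Day 28 mortality" among the data collected, but nothing links either to the recovery curve.

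**The concern.** Section 9.4 names a method and a quantity that agree only under a condition it does not state. Cumulative incidence of recovery is the share of all randomized patients who have recovered by a given day. Kaplan-Meier with deaths censored instead treats each dead patient as if they would have gone on to recover at the rate of the survivors. Its complement is therefore larger than the share recovered as soon as one recovery follows a death in the same arm. The two agree if patients who die stay in the risk set as not recovered through Day 28, but the plan does not say that this will be done.

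Two things are at stake. First, the level: a curve that censors deaths does not show what proportion recovered, which is the form in which Section 9.1.2 states its expectation. Second, the contrast: an arm that loses recoveries because more of its patients die can show the same curve as placebo, or a better one.

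**Working it through.** **Inputs.** Recovery by Day 28 on placebo: 30% (9.1.2). Patients per pooled arm: 20 (9.1.2). Deaths by Day 28 in Phase I: days 7 and 27, so 2 of 10 = 20% (3.6). ARDS mortality: 30-60% (synopsis), with no time window. Using that range as Day-28 mortality is an assumption, as is treating all these deaths as deaths before recovery.

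**The plan's own calculation.** Section 9.1.2 gives log-rank power of 54% at a hazard ratio of 2.0 and 76% at 2.5. With an exponential placebo hazard of -ln(0.70)/28 per day, 365 days of uniform accrual plus 28 days, and no deaths, the Lakatos method gives 53.0% and 75.8%. The plan's figures are thus reproduced without any deaths, although with follow-up of 28 to 393 days per patient, which is a separate matter.

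**Overstatement within an arm.** Let r be the proportion recovered and d the proportion dead before recovery by Day 28, with constant cause-specific hazards:

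- total cumulative hazard H = -ln(1 - r - d)
- cumulative recovery hazard Hr = H × r/(r + d)
- curve with deaths censored, at Day 28: 1 - exp(-Hr)

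With r = 0.30:

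| d | H | Hr | Curve shows | True |
|---|---|---|---|---|
| 0.20 | 0.693 | 0.416 | 34.0% | 30% |
| 0.30 | 0.916 | 0.458 | 36.8% | 30% |
| 0.40 | 1.204 | 0.516 | 40.3% | 30% |
| 0.50 | 1.609 | 0.604 | 45.3% | 30% |
| 0.60 | 2.303 | 0.768 | 53.6% | 30% |

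Simulation with 20 patients per arm (20,000 runs) agrees: means of 34.1%, 36.7%, 40.3% and 53.0% at d = 0.20, 0.30, 0.40 and 0.60.

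**Without the constant-hazard assumption.** Take 20 patients, 6 recoveries and 4 deaths. If all deaths come after the last recovery, the curve ends at 6/20 = 30%. If all come before the first recovery, it ends at 6/16 = 37.5%. Timing alone decides where it falls. In a single product arm of 10, 3 recoveries after 3 early deaths show 3/7 = 43%, not 30%.

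**Between arms, death hazard doubled and recovery hazard unchanged.** The proportion recovered is Hr/(Hr + Hd) × [1 - exp(-(Hr + Hd))].

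- From 30% recovered and 30% dead: Hr = 0.458, and Hd goes from 0.458 to 0.916. Recovered becomes 24.9% and dead 49.8%. Both curves end at 36.8%.
- From 30% recovered and 20% dead: Hr = 0.416, and Hd goes from 0.277 to 0.555. Recovered becomes 26.6% and dead 35.5%. Both curves end at 34.0%.

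**Between arms, equal recovery.** If 30% recover in both arms but 30% versus 50% die, the extra deaths being among patients who would not have recovered, the curves show 36.8% versus 45.3%. The cumulative recovery hazards are 0.458 and 0.604, a ratio of 1.32 in favour of the arm with more deaths.

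**A reversal with whole patients.** Placebo: 6 recoveries (days 10, 13, 16, 20, 23, 26) and 4 deaths (days 9, 12, 15, 18). Survival without recovery is 18/19 × 16/17 × 14/15 × 12/13 × 11/12 × 10/11 = 0.640, so the curve shows 36.0%. Treatment: 8 deaths by Day 10, then 5 recoveries from 12 at risk, so the curve shows 5/12 = 41.7%. True recovery is 30% versus 25%. Holding the deaths in the risk set to Day 28 returns exactly 30% and 25%.

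**Scale.** The standard error of a difference with 20 per arm is sqrt(2 × 0.3 × 0.7/20) = 0.145, about 14 points.

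**The case against.** The strongest reply is that the plan never says deaths will be censored. It names cumulative incidence, so the team may intend to hold deaths as not recovered, in which case the curve is right. That is possible, and it is why the rule should be written down: censoring is what a standard Kaplan-Meier routine does unless told otherwise.

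Second, the larger figures rest on 40-60% mortality by Day 28, which the documents do not give. This stands. The only dated figure is Phase I. Scaling its timing to 20 patients (2 deaths on Day 7, 2 on Day 27, 6 recoveries by Day 27) gives 6/18 = 33.3% if all recoveries follow Day 7. If three precede Day 7, it gives 1 - (17/20 × 12/15) = 32.0%. That is an excess of 2 to 3 points, small beside a 14-point standard error. Phase I is only 10 patients, however, and the excess is systematic.

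Third, survival is reported separately, so a large difference in deaths would be seen. This is partly right: the loss is hidden in the recovery plot, not necessarily in the whole report. But the endpoint list in Section 3.3 omits survival, and a separate survival figure does not correct the recovery curve.

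Fourth, equal curves are the correct answer about the hazard of recovery when only the death hazard changes. That is true, but 9.4 says it compares cumulative incidence.

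Fifth, the 30% is an expectation from unseen research, not a planned comparator, and might itself be a Kaplan-Meier estimate. Fair, but it is worded as a proportion of patients, and readers will set the placebo curve against it.

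Finally, safety is the trial's primary endpoint and the efficacy analysis is descriptive. That limits the consequence. It also makes the plot itself the efficacy result, with no planned test in 9.4 to correct a misleading picture.

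**Conclusion.** The concern holds. The documents give no rule for deaths in the analysis of the primary efficacy outcome, and ordinary Kaplan-Meier censoring does not estimate the cumulative incidence that 9.4 names. Against a true 30%, the overstatement is about 4 points at the Phase I mortality of 20%, and 7 to 24 points if Day-28 mortality lies in the quoted 30-60% range. A doubling of the death hazard alone can remove 3 to 5 points of recovery with no visible change in the curve.

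These sizes rest on three assumptions: deaths are censored at death, hazards are constant over 28 days, and the mortality values apply by Day 28 to patients not yet recovered. Early deaths enlarge the bias, and deaths after the last recovery add none. It should be fixed before the analysis. It does not threaten the safety objective or any formal test.

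**What to change.** In Section 9.4, replace the Kaplan-Meier estimate with the Aalen-Johansen cumulative incidence of recovery to Day 28, taking death before recovery as the competing event. With complete follow-up it is equivalent to keep patients who die in the risk set as not recovered through Day 28; either rule will do if it is stated. Plot the cumulative incidence of death by arm beside it, for the pooled comparison and for each product arm. Gray's test or a subdistribution hazard ratio is optional. Any log-rank test or hazard ratio that censors deaths should be labelled cause-specific and shown with the death curves.

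The cost is one or two sentences and standard software. Day 28 mortality and hospital discharge are already collected under Section 6.1.1.

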10 ETHICS/PROTECTION OF HUMAN SUBJECTS

10.1 ETHICAL CONDUCT OF TREATMENT PLAN

The treating physician is responsible for the conduct of this treatment plan in accordance with of the U.S. Code of Federal Regulations Title 21 Parts 50, 56, and 312, and the ethical principles originating from the Declaration of Helsinki. The treating physician is responsible for personally overseeing the treatment of the patient. The treating physician must assure that all clinical staff members, adhere to the treatment plan protocol and all FDA/GCP/NCI regulations and guidelines regarding single patient use/expanded access for an investigational agent.

10.2 INSTITUTIONAL REVIEW BOARD

This treatment protocol is being reviewed by the Western Institutional Review Board (IRB) and will be the IRB of record.

The protocol, informed consent form, and any patient materials will be submitted to the Institutional Review Board (IRB) of record for review before the patient is treated.

10.3 DATA AND SAFETY MONITORING BOARD

Safety will be overseen by a Data and Safety Monitoring Board (DSMB) throughout the duration of study conduct. At any time, the DSMB may recommend that dosing be modified or enrollment stopped due to safety concerns. The DSMB may also request to receive additional data unblinded to the subject level in response to identified safety concerns. Routine meetings are to be scheduled as determined by the DSMB. Ad hoc meetings will be convened if needed in response to safety concerns. The DSMB Charter will describe the composition of the DSMB and safety monitoring details, as well as the frequency of meetings needed as the study progresses.

Members of Board

[name] The University of Arizona Health Sciences <[contact]> [contact]

[name] University of Texas MD Anderson Cancer Center <[contact]> [contact]

[name] Mayo Clinic <[contact] [contact]

10.4 INFORMED CONSENT PROCESS

10.4.1 CONSENT AND OTHER INFORMATIONAL DOCUMENTS PROVIDED TO PATIENTS

A consent form describing in detail the investigational agent, treatment procedures, and risks are given to the patient or their legally authorized representative (LAR) and written documentation of informed consent is required prior to starting this treatment protocol. The consent form will include all the relevant elements currently required by the FDA Regulations and local or state regulations. Once this essential information has been provided to the patient and the treating physician is assured that the patient understands the implications of participating in this treatment protocol, the patient will be asked to give consent to participate in the treatment plan by signing the consent form. Prior to the patient's participation, the written informed consent form should be signed and personally dated by the patient, or the legally authorized representative (LAR), and by the person who conducted the informed consent discussion.

If a subject or LRA is unable to connect in person with study personnel, the following methods can be used to obtain informed consent that meets the requirements of local regulations, ICH guidelines,

and the IRB/EC or study center, where applicable:

 Review of the informed consent process will be provided via telehealth, phone, and/or videoconference (zoom health) in alignment with local regulatory guidance. During the remote informed consent process the subject, a witness, and someone from the study team will be present.

Signatures of the informed consent can be obtained in any of the following ways:

- Electronically (Docusign or Adobe Certificate); OR
- Secure email or picture of the signed informed consent. This does not preclude a site from obtaining consent via paper, if such arrangements can be made, e.g. fax, mail.

The following consent materials are submitted with this protocol:

Adult Informed Consent Form.

10.4.2 CONSENT PROCEDURES AND DOCUMENTATION

Informed consent is a process that is initiated prior to the patient's agreement to participate in the treatment protocol and continues throughout the patient's participation. Extensive discussion of risks and possible benefits of participation will be provided to the patient. Consent forms will be IRB- reviewed and the patient will be asked to read and review the document. The treating physician, or designee, will explain the treatment plan to the patient and answer any questions that may arise. The patient will receive a verbal explanation in terms suited to their comprehension of the purposes, procedures, and potential risks of the treatment and of their rights as a patient. He will have the opportunity to carefully review the written consent form and ask questions prior to signing. The patient should have the opportunity to discuss the treatment with his surrogates or think about it prior to agreeing to participate. The patient will sign the informed consent document prior to any procedures being done specifically for the treatment plan. The patient may withdraw consent at any time throughout the course of the treatment. A copy of the informed consent document will be given to the patient for their records. The rights and welfare of the patient will be protected by emphasizing to him that the quality of their medical care will not be adversely affected if they decline to participate in this treatment protocol.

